3.2 L-asparaginase in AML treatment

L-asparaginase activity is based on its catalytic activity for degrading asparagine and glutamine in blood and tissue liquids into aspartic and glutamic acid and ammonia, which thus induce a cytotoxic response against asparagine-dependent tumors. Survival and growth of most of leukemic cells, such as lymphoblasts as well as certain solid cancer cell lines, are asparagine-dependent, using this amino acid as nutriment for protein synthesis. This degradation is mainly evidenced by their asparagine depletion levels. This asparagine depletion results in a regression of leukemic cell proliferation (Broome, 1981) by several mechanisms involved in the destruction of tumor cells following treatment: inhibition of protein biosynthesis and subsequently, induction of apoptosis (Story, 1993).

Conversely, normal cells are resistant to L-asparaginase as they can synthesize asparagine using asparagine synthetase (ASNS) from other amino acids (glutamine or aspartic acid) when the level of serum asparagine is lowered. However some cancer cells are lacking ASNS and therefore when they are deprived of L-asparagine for growth and DNA replication, they become apoptotic and die.

A potential interest in AML has been identified from therapeutic use of free L-asparaginase and some bibliographic data. It has been demonstrated that AML blasts, especially M5 subtype cells, display a low level of ASNS (Codegoni 1995; Dubbers 2000; Kaspers 1999 Zwaan 2000). Kitoh *et al.* (1996) performed immunocytochemical staining in AML samples and showed that FAB M1, M4 and M5 cells were negative for ASNS. This supports the results of Okada *et al.* (2003) showing the relative sensitivity of M1, M4 and M5 cells to L-asparaginase and strongly suggests that ASNS expression is inversely correlated with sensitivity to L-asparaginase in AML cells.

Several cooperative groups have studied the combination of L-asparaginase with other induction chemotherapy regimen used in first-line and relapse AML, both in adults and in children. In adults, Capizzi (1988) has reported a significant benefit of L-asparaginase in AML. One hundred ninety-five adult patients with refractory or first AML relapse were randomly assigned to receive high-dose cytarabine (HiDAC), 3 g/m² as a three-hour intravenous (IV) infusion every 12 hours for four doses, followed by L-asparaginase 6,000 IU/m² (L-Asp) administered at hour 42, or HiDAC without L-Asp. Treatment was repeated on day 8. There was an overall superior complete remission (CR) rate for HiDAC/L-Asp (40%) vs HiDAC (24%), P = .02. Subset analysis according to prior response and age showed the following CR rates: 54% from HiDAC/L-Asp treatment of refractory AML in patients less than 60 years, and 31% in patients greater than 60 years; CR from HiDAC in the same refractory groups were 18% (less than 60) and 0% (greater than 60). There was an overall survival benefit for patients treated with HiDAC/L-Asp (19.6 weeks) compared with HiDAC (15.9 weeks), P = .046, primarily attributable to effects in refractory patients. Toxicity in the two treatment arms was comparable.

Another pilot study with high-dose cytarabine plus asparaginase in elderly patients with acute nonlymphocytic leukemia newly diagnosed has been performed by the Italian Cooperative Group GIMEMA (Petti *et al.*, 1989). Overall 43/125 evaluable patients (34.4%) achieved CR. In addition a synergistic efficacy of L-asparaginase with cytarabine when used sequentially has been observed in this study.

The Children Oncology Group (COG) published a review (Wells *et al.*, 1993) to determine the impact of highdose cytarabine and L-asparaginase intensification on the outcome of childhood AML. Three consecutive Children Cancer Group (CCG) trials in AML: CCG 251 (1979 to 1983), CCG 213P (1983 to 1985), and CCG 213 (1985 to 1989) with a total of 1,294 patients enrolled, were reviewed. Inclusion of the 7-day interval cytarabine/L-asparaginase intensification was accompanied by an overall improvement in 5-year survival rates from diagnosis when compared with historical controls (CCG 213, 36% vs CCG 251, 29%, P < .02).

In children, L-Asparaginase is currently used in AML treatment protocols (protocol ELAM 02 2010).

Others single case reports have been published recently, pointing out the potential benefit of L-asparaginase in different AML or mixed lineage leukemia (Horikoshi *et al.*, 2009, Rubnitz *et al.*, 2009, Takahashi *et al.*, 2012).

3.3 GRASPA, a new formulation of L-asparaginase

GRASPA is a 'circulating microbioreactor'. As shown in Figure 2, plasma asparagine is actively pumped through the membrane of the erythrocyte into the intracellular compartment where it is cleaved by entrapped L-asparaginase. The erythrocyte membrane protects L-asparaginase against fast degradation/elimination, hence allowing for a long circulating activity and a longer half-life than with free L-asparaginase. Thus, GRASPA combines the capacity of erythrocytes to actively 'pump' asparagine from blood plasma through sodium-coupled neutral amino acid transporters and the enzymatic activity of entrapped L-asparaginase to cleave asparagine into aspartic acid and ammonium leading to plasma asparagine depletion. This encapsulation concept is not considered as a 'slow release' of the L-asparaginase, since the activity of asparagine degradation takes place within the erythrocyte, until the latter is removed in the same manner as normally transfused erythrocytes, by macrophages or dendritic cells in the liver or spleen. The encapsulation of L-asparaginase eliminates the direct somatic contact with the L-asparaginase, and it is hypothesized that this provides the potential to reduce toxicity associated with the parent L-asparaginase and prolong the activity of the enzyme (Figure 2).

Several tumor types depend on circulating asparagine for their growth and survival. In particular, leukemic cells are deficient in asparagine synthetase enzyme and are therefore incapable of synthesizing asparagine

(Stams *et al.* 2005, Kumar *et al.* 2014). The L-asparaginase treatment is based on the conversion of circulating asparagine into aspartic acid and ammonia, which deprives cancer cells of their source of asparagine and leads to their growth arrest and apoptosis. Normal cells are protected from asparagine requirement due to their ability to produce this amino acid with the help of the ASNS (Kawedia and Rytting 2014).

Figure 2: Mechanism of action of GRASPA

One main advantage of encapsulating L-asparaginase into erythrocytes is to reduce hypersensitivity reaction to asparaginase, as the L-asparaginase is protected from the immune system by the erythrocyte membrane. Additionally, its active site is preserved, potentially resulting in lower production of neutralizing antibodies and reduction in the frequency and severity of hypersensitivity reactions. Although the enzyme retains its intrinsic immunogenic potential, it is no longer expressed as the erythrocyte membrane prevents its recognition by the immune surveillance systems of the host.

3.4 GRASPA Current Clinical Experience

Four clinical trials have been conducted with GRASPA in Europe, in pediatric, adult and elderly patients with ALL – Table 1.

Study reference	Type of study /population	Status
	GRASPALL 2005-01: Administration of allogenic red blood cell-loaded L-asparaginase in patients with relapsed acute lymphoblastic leukemia (ALL)	Completed
GRASPALL 2005-01	A Phase I/II multicenter, randomized study in adults and children over 1 year of age.	
	N= 24 patients (GRASPA:9 children and 9 adults; native apsaraginase:3 children and 3 adults)	
GRASPALL GRAALL SA2 2008	An escalating dose Phase IIa study of GRASPA added to multi-agent chemotherapy during induction phase for the	Completed

 Table 1:
 Clinical trials with GRASPA in ALL indication

- CONFIDENTIAL -

	treatment of elderly patients, aged 55 years and over, presenting with Philadelphia chromosome-negative ALL. N= 30 patients	
GRASPALL 2009-06	A multicenter, open, randomized, Phase IIb/III study, evaluating efficacy and safety of GRASPA versus native L- asparaginase treatment in combination with multi-agent chemotherapy in patients with first recurrence of Philadelphia chromosome negative ALL N=80 patients (54 children and 26 adults). The randomized arms, n= 54 (GRASPA = 26; native asparaginase = 28)	Completed
GRASPALL2012-10- EAP Expanded Access Program	A multicenter, open, non-randomized study, evaluating safety of GRASPA in combination with multi-agent chemotherapy in patients under 55 years old with ALL at risk to receive other formulation of asparaginase.	Ongoing (13 patients enrolled)

The pivotal Phase III trial (GRASPALL 2009-06) is a randomized controlled trial, Figure 3.

Figure 3: GRASPALL2009-06 Study diagram

The co-primary endpoints were:

- 1. Duration (in days) of L-asparaginase activity >100 IU/L; and
- 2. Occurrence of study drug-related allergic reactions during the induction phase.

Key secondary endpoints included: MRD, complete remission rate, anti-asparaginase antibodies, adverse events, Events Free Survival and OS.

This trial enrolled 80 patients aged from 1 to 55 years, with either first relapse of Ph-ALL, or refractory to first-line treatment, and who were previously treated with native *E. Coli* L-asparaginase.

The mean duration of asparaginase > 100 IU/L measured in whole blood was significantly higher in GRASPA arm compared to control arm, with a mean (\pm SD) of 20.5 (5.2) days and 9.4 (7.4) days, respectively, p = 0.001. None of the patients (0/26) in the GRASPA arm had hypersensitivity reactions related to study drug during induction, compared to 13 (46.4%) in the control arm, p = 0.001. Patients in GRASPA arm achieved a higher CR (65.4%, 95% CI: [51.6:89.8]) as compared to control arm (39.3%, 95% CI: [23.3:63.1]), p=0.026.

The key adverse events of interest, generally considered to be a class-effect relevant to L-asparaginase, mainly included hypersensitivity reactions, coagulopathic events, pancreatic and hepatic events. The majority of these events occurred at a lower frequency with GRASPA compared to L-ASP, Table 2.

Table 2: Summary of key adverse events of interest that are study-related AEs in ≥ 10% of patients arranged by MedDRA Preferred Term

Preferred Term [a]	GRASPA N=26 (%)	Control native asparaginase N= 28 (%)
At least one AE	19 (73.1)	28 (100)
Hypofibrinogenemia	7 (26.9)	18 (64.3)
Elevated amylase and/or lipase enzyme elevation)	7 (26.9)	15 (53.6)
Transaminase increased	5 (19.2)	6 (21.4)
Hypoalbuminemia	4 (15.4)	9 (32.1)
Anti-thrombin III decreased	3 (11.5)	20 (71.4)
Hyperbilirubinemia	2 (7.7)	5 (17.9)
Drug hypersensitivity reactions	2 (7.7)	16 (57.1)
Hepatotoxicity	1 (3.8)	5 (17.9)
GGT increased	1 (3.8)	4 (14.3)
Activated partial thromboplastin time prolonged	1 (3.8)	3 (10.7)

Extras of Table 14.3.1.10.1 GRASPALL 2009-06 CSR

4. Objectives

4.1 Primary objective

To evaluate Overall Survival (OS) in AML patients 65-85 years old and unfit for intensive chemotherapy, when treated with GRASPA plus low-dose cytarabine compared to low-dose cytarabine alone.

4.2 Secondary objectives

- Response to treatment
- Progression-free survival
- Relapse Free Survival
- Patient transfusion needs
- Patients Quality of life evolution
- Number of hospitalizations
- Safety of GRASPA in combination with cytarabine
- Pharmacokinetic and pharmacodynamic parameters of GRASPA
- Immunogenicity of GRASPA
- Asparagine Synthetase (ASNS) expression and sensitivity to L-asparaginase in bone marrow cells (optional)
- Biomarker cytogenetic testing (optional)

4.3 Study endpoints

4.3.1 Primary endpoint

Overall survival (OS) is defined as the time elapsed between randomization and death for any cause. Patients not known to have this event are censored on the date they were last examined.

4.3.2 Secondary endpoints

- Percentage of patients with Complete remission (CR), Complete remission with incomplete recovery (neutrophil or platelet regeneration, CRi), Partial remission (PR)
- Progression-free survival (PFS) defined as the time elapsed between randomization and resistant disease or relapse or death from any cause
- Relapse Free Survival defined only for patients who achieved CR or CRi as the time elapsed between date of CR/CRi and date of disease relapse or death from any cause
- Percentage of patients who need transfusions (red blood cells and/or platelets), number of transfusions by patient
- Patient quality of life evaluated using the EORTC QLQ-C30 version 3 scale
- Number of hospitalizations (except scheduled protocol visit) required during the study
- Safety of GRASPA in combination with low-dose cytarabine, with specific attention to :
 - o Grade 3 or 4 of Pancreatic toxicity
 - o Grade 3 or 4 of hepatic toxicity, allergic reaction or coagulation event
 - o Grade 3 or 4 of hypoproteinemia or hyperglycemia/diabetes
 - All other non-hematologic Grade 4 toxicities

(*NB* grading reference used: NCI CTCAE version 4.0)

- Pharmacokinetic and pharmacodynamic parameters:
 - o Plasma concentrations of asparagine, aspartate, glutamine, glutamate
 - Whole Blood L-asparaginase activity
- Immunogenicity by measuring titer of anti-L-asparaginase antibodies
- Biomarker cytogenetic testing (optional)
- Measurement of the following parameters on harvested bone marrow tumor cells (optional):
 - Asparagine synthetase protein expression
 - Asparagine synthetase mRNA expression
 - In vitro sensitivity to L-asparaginase

(See also section 8.8 for details)

Table 3 hereafter provides the definitions of response criteria in AML.

Category	Definition
Complete remission (CR)*	Bone marrow blasts < 5%; absence of blasts with Auer rods; absence of extramedullary disease; absolute neutrophil count > $1.0 \times 10^{9}/L$ (1000/µL); platelet count > $100 \times 10^{9}/L$ (100 000/µL); red blood cell transfusion independence
CR with incomplete recovery (CRi)	All CR criteria except for residual neutropenia ($< 1.0 \times 10^{9}/L [1000/\mu L]$) or thrombocytopenia ($< 100 \times 10^{9}/L [100 000/\mu L]$)
Partial remission (PR)	all hematologic criteria of CR; decrease of bone marrow blast percentage to 5% to 25%; and decrease of pre-treatment bone marrow blast percentage by at least 50%
Resistant disease (RD)	BM blasts increase of at least 5% vs nadir AND/OR PBBC increase of at least 15% in absolute count vs nadir OR at least 50% in percentage vs nadir – repeated at min 7 days interval
Relapse¶	Bone marrow blasts \geq 5%; or reappearance of blasts in the blood; or development of extramedullary disease
Stable disease	Failure to achieve at least Partial Remission AND no Resistant Disease criteria

Table 3: Response criteria in AML

* All criteria need to be fulfilled; marrow evaluation should be based on a count of 200 nucleated cells in an aspirate with spicules; if ambiguous, consider repeat exam after 5 to 7 days; flow cytometric evaluation may help to distinguish between persistent leukemia and regenerating normal marrow; a marrow biopsy should be performed in cases of dry tap, or if no spicules are obtained; no minimum duration of response required. ¶ In cases with low blast percentages (5-10%), a repeat marrow should be performed to confirm relapse. Appearance of new dysplastic changes should be closely monitored for emerging relapse. In a patient who has been recently treated, dysplasia or a transient increase in blasts may reflect a chemotherapy effect and recovery of hematopoiesis. Cytogenetics should be tested to distinguish true relapse from therapy-related MDS/AML. (adapted Döhner *et al* 2010, Diagnosis and management of acute myeloid leukemia in adults: recommendations from an international expert panel, on behalf of the European LeukemiaNet, Blood, 21 Jan 2010, vol 15, no 3; 453 - 474)

5. Benefit – risk analysis

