8.6 AML assessment

Initial bone marrow aspirate/biopsy must be available within four weeks prior randomization, for baseline blast count.

AML assessment will be performed for each course, in order to allow AML disease evaluation and response to treatment based on adapted Dohner criteria (see Table 3 for Response criteria definitions)

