8.7 Laboratory assessments

8.7.1 Biological parameters

Biological assessment will be performed according to the investigational center procedure at inclusion, and then, at D1, D5, D9, D13, D18, D23 and D27 of each course of chemotherapy (± 2 days).

Following measurement should be performed:

- Hematology: Complete Blood Count (CBC), platelets;
- Coagulation parameters: Prothrombin Time (PT), activated Partial Thromboplastin Time (aPTT), fibrinogen, antithrombin III, INR;
- Chemistry: bicarbonate, sodium, potassium, calcium, creatinine, creatinine clearance (calculated by Cockroft & Gault formula), albumin, bilirubin, alanine amino transferase (ALT), aspartate amino transferase (AST), alkaline phosphatase, gamma glutamyl transpeptidase (GGT), lactate dehydrogenase, glucose, cholesterol, triglyceride, lipase, amylase;
- Serologic test for HIV, B and C hepatitis will be made at inclusion only, if needed.
- Serum pregnancy test for women with childbearing potential at inclusion and end of treatment.

Assessed and signed anonymized lab reports must be sent to sponsor/representatives as soon as possible after receiving the results for protocol required tests as well as for any testing performed for management of AEs.

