3.5. Efficacy, Pharmacokinetic, and Safety Variables

3.5.1. Efficacy Variables

The primary objective of this study is to evaluate the efficacy and tolerability of GRASPA when combined with LDAC. The primary endpoint is overall survival (OS), defined as the time elapsed between randomization and death for any cause. Patients not known to have this event are censored on the date they were last examined.

Secondary efficacy endpoints include the following:

- 1) Complete remission (CR), Complete remission with incomplete recovery (neutrophil or platelet regeneration, CRI), Partial remission (PR)
- 2) Progression-free survival (PFS) defined as the time elapsed between randomization and resistant disease or relapse or death from any cause
- 3) Relapse Free Survival defined only for patients who achieved CR or CRI as the time elapsed between date of CR/CRI and date of disease relapse or death from any cause
- 4) Percentage of patients who need transfusions (red blood cells and/or platelets), number of transfusions by patient
- 5) Patient quality of life evaluated using the EORTC QLQ-C30 version 3 scale
- 6) Number of hospitalizations (except scheduled protocol visit) required during the study

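### The protocol and SAP define the PFS progression event by conflicting rules, and the protocol's 5% marrow rise over nadir lies within the counting error of a 200-cell marrow

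*Protocol*

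**What the plan says.** - **Event rule, protocol 4.3.2, Table 3.** Resistant disease is "BM blasts increase of at least 5% vs nadir AND/OR PBBC increase of at least 15% in absolute count vs nadir", continued by "OR at least 50% in percentage vs nadir – repeated at min 7 days interval". Stable disease is what remains: "Failure to achieve at least Partial Remission AND no Resistant Disease criteria".
- **Use in PFS.** Protocol 4.3.2 has "Progression-free survival (PFS) defined as the time elapsed between randomization and resistant disease or relapse or death from any cause", and protocol 15.3.3 names the same events. SAP 3.5.1 repeats "time elapsed between randomization and resistant disease or relapse or death from any cause".
- **A second rule, SAP 5.6.2.2.** The section that specifies the PFS analysis takes progression from the eCRF disease-evaluation page. It requires a marrow blast rise of at least 25% or a blood blast rise of at least 50%, both against baseline, or extramedullary disease. Potential events are reviewed before database lock, but no review criteria are given. SAP Table 4 has no row for resistant disease.
- **Counting and timing.** The footnote to the CR row of Table 3 says "marrow evaluation should be based on a count of 200 nucleated cells in an aspirate with spicules". Protocol 8.6 says "AML assessment will be performed for each course". Protocol 8.7.1 schedules blood tests "at D1, D5, D9, D13, D18, D23 and D27 of each course of chemotherapy".
- **Role of PFS.** OS is primary and PFS secondary. The SAP introduction says that activity will be judged over a range of endpoints and not on the primary analysis alone.

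**The concern.** There are two linked problems.

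First, the documents give PFS two different progression events. One is referenced to nadir and the other to baseline, with different limits and different provisions for confirmation. Two programmers could follow the text and produce different PFS data sets.

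Second, the Table 3 rule asks for a small rise over the lowest earlier value. Each marrow reading is a finite count, and the minimum of several noisy readings drifts downward as readings accumulate. A patient whose disease has not changed can therefore meet the rule by chance. A repeat judged against the same low nadir reduces these calls but does not remove them. False events of this kind occur in both arms and pull the PFS hazard ratio toward 1, which weakens an endpoint that the SAP means to use as supporting evidence.

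**Working it through.** **1. The plan's own figure.** Protocol 15.2 states 117 PFS events for 80% power, two-sided 5%, 2:1 allocation. Medians of 2 and 3.5 months (SAP 5.1) give HR = 2/3.5 = 0.571. Power = Φ(√(117 × 2/9) × |ln 0.571| − 1.96) = 81%, so the figure is reproduced; the same formula needs 113 events for 80%. The documents give no error rate for the resistant-disease rule.

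**2. Error of one pair of marrows.** Assume 200 cells per count (the CR footnote, applied to resistant disease by inference) and an unchanged true blast share p. The SE of one count is √(p(1−p)/200), and the 95% limit for a difference of two counts is 1.96 × √(2p(1−p)/200).

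| p | SE of one count | 95% limit for a difference | P(second ≥ first + 5 points) |
|---|---|---|---|
| 20% | 2.8 points | 7.8 points | 12% |
| 30% | 3.2 points | 9.0 points | 15% |
| 50% | 3.5 points | 9.8 points | 17% |

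Five points lies inside the limit once p exceeds about 7%.

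**3. Running nadir with confirmation.** Simulation of 200,000 patients with constant p: one baseline marrow, then one per course, nadir equal to the lowest earlier value. A call needs a rise at one marrow and again at the next, both against the same nadir, and is counted when confirmed.

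| Rule | p | By third later marrow | By sixth |
|---|---|---|---|
| +5 points | 20% | 9% | 29% |
| +5 points | 30% | 13% | 38% |
| +5 points | 50% | 16% | 44% |
| +5% relative | 20 / 30 / 50% | 47 / 44 / 35% | – |
| +10 points | 20–50% | 0.2–1.2% | 1–5% |

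Without any repeat, +5 points gives 42–55% by the third marrow. These rates are conditional on remaining stable and under observation. At the planned medians, six courses (5.5 months) leave 0.5^(5.5/2) = 15% and 0.5^(5.5/3.5) = 34% event-free, so the sixth-marrow column concerns a minority.

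**4. Blood limb.** The documents give no precision for blood blasts. Assume a 100- to 200-cell differential, a constant white count, end-of-course samples only and the same confirmation.

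- 15% read as relative: 36–49% false calls by the third sample at 5–10% blasts. At 50% blasts with 200 cells it is about 7%.
- 15 points: essentially none at 5–10% blasts, and at most 2% by the third sample at 50%.
- A nadir of zero leaves the relative limbs undefined.

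**5. The SAP rule.** Read as a relative 25% rise over baseline, one pair of 200-cell counts meets it by chance in 14, 7.5 and 1.4% of cases at 20, 30 and 50% blasts. Without a repeat and before review, this becomes 28, 16 and 4% by the third later marrow. It behaves differently from Table 3 but is not free of the problem.

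**6. Effect on the hazard ratio.** Let a fraction r per 28-day course have a false event in either arm, with h = −ln(1−r)/(28/30.44) per month. Then HR = (ln2/3.5 + h)/(ln2/2 + h).

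- r = 5%: h = 0.056; 0.254/0.402 = 0.63.
- r = 10%: h = 0.115; 0.313/0.461 = 0.68.

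As a guide to r, the confirmed marrow rates in step 3 average about 3–6% per course over three marrows (for example 1 − 0.87^(1/3) = 4.5%) and 6–9% over six (1 − 0.62^(1/6) = 7.7%).

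**The case against.** The strongest reply is that SAP 5.6.2.2 is the operative text. It has no nadir, no 5% and no 15% limit, and it provides for review before lock, so Table 3 events may never enter the PFS analysis. That is a fair reading, but it does not settle the matter. SAP 3.5.1 and protocol 15.3.3 still name resistant disease, and only Table 3 defines it.

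Two further limits stand. The 200-cell count belongs to the CR footnote, although no other marrow count is specified. Version 7 redefined the response criteria in October 2015, while recruitment was planned from early 2013 over 36 months, so not every PFS event need have been scored by this rule.

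A reader might infer more than the documents support:

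- **That nearly every stable patient becomes resistant through the blood limb.** This needs all seven draws per course to feed the nadir, a relative reading of 15% and a small differential count. AML assessment is once per course, and the other two points are not stated.
- **That false calls reach 13, 21 and 46% by courses 2, 3 and 6 at 30% blasts.** This dates each event at the first rise and so runs one course ahead of confirmation. Table 3 does not state that dating.
- **That the trial loses its power.** The 117 events and 80% power belong to PFS as the former primary endpoint.
- **That overlap with partial remission is an error.** A patient falling from 60% to 10% and rising to 16% meets the marrow rise while still inside the marrow part of PR. Any nadir-based rule set beside a baseline-based response can do this.

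**Conclusion.** The point holds in a bounded form. The two documents build PFS on conflicting events, and this rests on the text alone. Under the Table 3 rule, read favourably, about 9–16% of truly stable patients at 20–50% marrow blasts would be falsely called resistant, with confirmation, by the third later marrow, and 29–44% by the sixth if still stable and observed. A relative reading of 5% is far worse. The blood limb is exposed only if 15% is relative.

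The marrow rates rest on a 200-cell count and on counting error alone; variation in sampling and between readers would add to it. The shift in the PFS hazard ratio from 0.571 to 0.63 or 0.68 is an illustration at assumed false-event rates, not an estimate for this trial.

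OS and the decision based on its hazard ratio are untouched. The matter should be corrected because PFS contributes to the overall judgement of activity, but it does not threaten the primary result.

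**What to change.** Make these changes for the derivation of the PFS endpoint only, before database lock:

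1. Reconcile protocol 4.3.2 (including Table 3) and 15.3.3 with SAP 3.5.1 and 5.6.2.2, and name one governing progression rule.
2. State the marrow rise in percentage points and set it above counting error. Ten points, for example, gives 0.2–1.2% confirmed false calls by the third marrow and 1–5% by the sixth. At minimum, pre-specify this as a PFS sensitivity analysis.
3. Take nadir and rise from the scheduled end-of-course AML assessment.
4. State that confirmation applies to the marrow limb, and whether the event is dated at the first rise or at confirmation.
5. State whether the 15% blood rise is relative or in points, and how a zero nadir is handled.

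The cost is wording and derivation code, with no additional marrow or visit. The downside is that some true progressions would be called up to one course later.

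Protocol 8.11 uses the same term for ending study treatment. That section must be reconciled with the endpoint definition; no treatment rule is proposed here.
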